Title: Comparing right colon adenoma and hyperplastic polyp miss rate in colonoscopy using water exchange and carbon dioxide insufflation: A prospective randomized controlled trial

INTRODUCTION

Colonoscopy is currently regarded as the gold standard to detect and prevent colorectal cancer (CRC) [1]. It is estimated to prevent about 76%-90% of CRC [2], but post-colonoscopy CRCs (PCCRCs) still occur. Recent case-control studies consistently demonstrated that protection by colonoscopy against right-sided colon cancer, ranging from 40% to 60%, was lower than the 80% protection attained in the left colon [3-5]. Of all PCCRCs, 58% were attributed to lesions missed during examination [6]. In a systematic review of tandem colonoscopy studies, a 22% pooled miss-rate for all polyps was reported [7]. Colonoscopy maneuvers helping to reduce miss-rate for all polyps, particularly in the right colon, have the potential to decrease the incidence of PCCRCs.

Water exchange (WE) colonoscopy is characterized by the gasless insertion to the cecum in clear water and maximizing cleanliness during insertion. WE colonoscopy has been shown to improve the overall adenoma detection rate (ADR), compared to air insufflation colonoscopy, in many prospective randomized controlled trials (RCTs) [8-13]. WE colonoscopy also has been shown to improve right colon ADR in RCTs [10-12] and meta-analyses [14,15]. In a pooled data from two multisite RCTs, WE also significantly increases right colon combined advanced and sessile serrated ADR as compared to air insufflation colonoscopy [16]. Decreased multitasking-related distraction from cleaning maneuvers has been the most recently identified explanation for the increase in ADR by WE [17]. The right colon is usually the worst prepared segment and proximal colorectal neoplasms with advanced histology

frequently are smaller than the ones in the left colon or have a nonpolypoid appearance [18,19]. Therefore, the adoption of WE in the right colon might be especially beneficial.

Traditionally, all CRC are believed to arise from the adenomas through the adenoma-carcinoma sequence. However, recent studies showed that 35% of CRC were derived from serrated lesions (SLs) [20], which include hyperplastic polyp (HP), sessile serrated adenomas/polyps (SSA/Ps) and traditional serrated adenomas [21]. The presence of SLs, even small and diminutive proximal HPs, has been reported to be associated with higher rates of synchronous advanced neoplasia [22,23]. Proximal HPs might also serve as precursors of cancer through DNA methylation and deficient DNA mismatch repair [24-26]. However, SLs tend to be pale and flat and pose a challenge for the endoscopists to detect them [27]. WE might come in handy for uncovering the proximal SLs through the above stated mechanisms.

The primary outcome of this study is the right colon combined adenoma miss rate (AMR) and hyperplastic polyp miss rate (HPMR) determined by tandem inspection of the right colon using WE or CO₂ insufflation for screening, surveillance, or positive fecal immunochemical test (FIT) indications. The secondary outcomes are the overall ADR and other adenoma detection related metrics between the two colonoscopy methods.

METHODS

This will be a prospective RCT comparing CO₂ insufflation and WE in terms of right colon combined AMR and HPMR by tandem inspection. It is originally designed as a multicenter study conducted in three community hospitals in Taiwan. Consecutive patients will be enrolled from April 2019 to October 2020. A written informed consent will be obtained from all participating patients. The study has obtained

ethical approval from the Joint Institutional Review Board of Taiwan (19-002-T-1) and has been registered with *ClinicalTrials.gov* (NCT03845933). Due to delay in obtaining IRB approval in two of the participating hospitals (Dalin Tzu-Chi Hospital obtained IRB approval in late May 2019 and has not recruited any patient; Taipei Medical University Hospital has not obtained IRB approval in early June 2019) and rapid recruitment of Evergreen General Hospital since April 2019, which has recruited and completed more than 90 patients in the end of May 2019, we have amended the study design from multicenter study to single center study and have obtained the approval of this amendment on July 19, 2019 from the Joint Institutional Review Board of Taiwan.

Participants

Consecutive patients aged 45 years or older undergoing colonoscopy for screening, surveillance, and positive FIT will be considered for enrollment [28]. Exclusion criteria will include familial adenomatous polyposis and hereditary non-polyposis CRC syndrome, personal history of CRC or inflammatory bowel disease, previous colonic resection, obstructive lesions of the colon, gastrointestinal bleeding, allergy to fentanyl or midazolam, American Society of Anesthesiology (ASA) classification of physical status grade 3 or higher (e.g. controlled congestive heart failure, stable angina, previous heart attack, poorly controlled hypertension, morbid obesity, chronic renal failure, bronchospastic diseases with intermittent symptoms), mental retardation, pregnancy, and refusal to provide a written informed consent.

Randomization

Patients will be randomized in a 1:1 ratio to undergo either the CO2 insufflation colonoscopy (CO2 group) or WE colonoscopy (WE group). Randomization will be carried out by a computer-generated random sequence. Stratification based on

colonoscopists and colonoscopy indications (screening, surveillance, and positive FIT) will be performed. Individual random sequence will be placed in an opaque envelope kept by an independent research assistant not directly involved in this study, which will be opened immediately before the procedure.

Bowel Preparation and Sedation

Patients will be instructed to eat low-residual foods for two days before colonoscopy. Oral and written instructions on the split-dose bowel preparation (Polyethylene glycol solution) will be provided to all patients. Colonoscopy will be performed without sedation or with moderate sedation (intravenous fentanyl plus midazolam). Moderate sedative agents will be administered by endoscopists.

Colonoscopy Procedures

Colonoscopies will be performed by two board-certified colonoscopists ([name], [name]). Standard colonoscopes (CF-Q260AL/I; Olympus Medical Systems Corp., Tokyo, Japan) will be used. All colonoscopists have performed more than 1000 conventional colonoscopies. Hands-on coaching by a WE expert ([name]) to standardize the WE method has been completed. Each colonoscopist has or will have completed 100 cases of WE learning curve. [name] will be involved in the study design, data analyses, and report preparation, but not in patient enrollment. All the colonoscopic procedures will be recorded.

Antispasmodic medication will not be administered during colonoscopy examination. CO₂ insufflation will be used for CO₂ group and the withdrawal phase of the WE group. Colonoscopy will begin with the patients in the left lateral position. In the WE group, the air pump will be turned off before starting the procedure. During the insertion phase, air and residual water or feces in the rectum will be aspirated, and then the colon will be irrigated with warm water (32C-35C) using

flushing pumps (Olympus AFU-100; Olympus Corp.). There will be no restriction placed on the overall volume of water infused to achieve adequate cleansing. Suction and infusion of water will be performed sequentially because the endoscope has only one channel. Air pockets, when encountered, will be aspirated. When the cecum is reached and after most of the water is suctioned to collapse the cecal lumen, CO2 will be opened. In the CO2 group, colonoscopy is performed in the usual fashion, with minimal insufflation required to aid insertion. Cleaning in the CO2 group will be performed entirely during withdrawal. In the CO2 group, suction marks will be deliberately produced in the hepatic flexure and cecum to mimic the same marks frequently produced by the WE technique. Cecal intubation will be defined as the passage of the scope tip beyond the ileocecal valve with visualization of the medial wall between the ileocecal valve and the appendix orifice.

Upon arriving at the cecum, CO2 insufflation will be used in both groups and the scope will be withdrawn from the cecum to the hepatic flexure, with inspection of the mucosa at the same time. All polyps identified will be resected and sent for pathology evaluation. The most distal part of the hepatic flexure will be marked by a forceps biopsy and then the scope will be reinserted into the cecum by the first endoscopist using CO2 insufflation. A tandem inspection of the right colon will then be performed by a second endoscopist blinded to the insertion method in both study groups. All polyps found herein will be counted as the missed polyps. After the second withdrawal to the mark of distal hepatic flexure, the remainder of the colon will be examined in a standard manner by the first endoscopist. To assess the adequacy of blinding, the second endoscopist will be asked at the end of tandem right colon examination to guess which insertion method has been used. If less than 66% of these answers are correct, then adequate blinding will be considered to have

been achieved.

Polyp search and resection will be performed during the withdrawal phase in both groups. Insertion polypectomy will not be performed. All proximal colon polyps will be removed irrespective of their size and appearance. All diminutive polyps with hyperplastic appearance (based on narrow band imaging) in the rectosigmoid colon will be documented by photography and left alone. Polyp size will be determined by comparison with an opened biopsy forceps or a snare.

In both groups, the following information will be recorded: bowel preparation quality using the Boston Bowel Preparation Scale (BBPS) score [29]; the total amount of sedative medications (in procedures with sedation); the length of colonoscopy reaching cecum; the amount of water infused and suctioned during insertion and withdrawal phases; the procedure time taken for insertion and withdrawal for the first examiner; the procedure time taken for tandem right colon inspection; the need of abdominal compression and/or positon change to assist colonoscopy insertion; the overall polyp number, size, histology and location; the missed right colon polyp number, size, histology and location.

Definition

Screening colonoscopy will be defined as either asymptomatic patients undergoing their first colonoscopic examination or patients with a history of negative screening colonoscopy undergoing their 5-year or 10-year follow-up examinations. Surveillance colonoscopy will be defined as patients with a history of colon polyps undergoing their follow-up examinations. Complete colonoscopy will be defined as successful cecal intubation. Insertion time will be defined as the time between the scope insertion and cecal intubation. Three stopwatches will be used to record the time taken for mucosal cleaning (water infusion and suction), mucosal inspection, and

polyp treatment respectively. Withdrawal time will be defined as the time from cecal intubation to the time when the colonoscope is withdrawn from the anus, including the time taken for mucosal cleaning, mucosal inspection, polyp biopsy and polypectomy. Total procedure time will be the sum of insertion time and withdrawal time. Three stopwatches will be used to record the time taken for mucosal cleaning, mucosal inspection, and polyp treatment, respectively, during the tandem right colon examination. Total duration of tandem right colon examination will be defined as the time of repeated examination from cecum to hepatic flexure by the blinded examiner, including the time taken for mucosal clearing, inspection and polyp treatment. Near-complete removal of infused water during insertion of WE is defined as $\geq 90\%$ removal of infused water. Inspection times by the first and second endoscopists will be recorded. Comparable inspection times in the study and control groups will support the use of equivalent withdrawal inspection methods.

All colonic polyps removed during procedures will be sent for histological examination with clear labeling of location and sequences of colonoscopy. The location of colonic polyps will be defined according to the anatomical distribution. Right colon will be defined as cecum, ascending colon, and hepatic flexure. Proximal colon will be defined as right and transverse colon. Diminutive polyps will be defined as polyps with size ≤ 5 mm. Small polyps will be defined as polyps with size 6-9 mm. Large polyps will be defined as polyps with size ≥ 10 mm. Adenomas will include all adenomas and sessile serrated adenoma. Advanced adenomas will be defined as those lesions with one of the following criteria: 1) lesions larger than 10 mm in diameter; 2) lesions with a villous component; 3) lesions with high-grade dysplasia; and 4) lesions with invasive features.

ADR will be defined as the proportion of colonoscopies with at least one adenoma.

Advanced ADR will be defined as the proportion of colonoscopies with at least one advanced adenoma. Mean adenoma per procedure (MAP) will be defined as the total number of adenomas detected divided by the number of colonoscopies. Mean adenoma per positive procedure (MAP+) will be defined as the total number of adenoma detected divided by the number of colonoscopies in which at least one adenoma is found. Mean additional adenomas detected beyond the first adenoma per positive procedure (ADR-Plus) will be defined as the mean number of adenomas detected after the first adenoma in procedures in which at least one adenoma is found.

Lesions detected on the tandem right colon examination will be used for the calculation of adenoma or polyp miss rate. Right colon AMR and hyperplastic polyp miss rate (HPMR) will be calculated as the number of adenomas and hyperplastic polyps missed in the first right colon examination divided by the total number of adenoma and hyperplastic polyps detected during both the first and tandem right colon examinations.

Study Outcomes

The primary outcome is the right colon combined AMR and HPMR. Secondary outcomes include right colon AMR, right colon HPMR, overall ADR, right colon ADR and HPDR after the first examination, combined right colon ADR and HPDR after the first and tandem examinations, overall advanced ADR, right colon advanced ADR, overall MAP, right colon MAP, overall MAP+, right colon MAP+, overall ADR-Plus, and right colon ADR-Plus. Procedure related parameters, including bowel cleansing, insertion and withdrawal times, duration of tandem right colon examination, volume of water infused and aspirated during insertion and withdrawal, and number of abdominal compressions and/or position change, are also evaluated.

Sample size estimation

The sample size estimation is based on the assumption that WE colonoscopy reduces right colon combined AMR and HPMR compared to conventional CO2 insufflation colonoscopy. We estimate the overall right colon combined AMR and HPMR in the CO2 group to be 30% [30,31]. According to our previous study, the average detected number of right colon adenoma and hyperplastic polyp is 0.8 per subject after first right colon examination [32]. To show a clinically important improvement of AMR reduction by the WE colonoscopy, we assume that WE colonoscopy should reduce the AMR by 15%. With a statistical power of 80% and a two-side significance level of 0.05, 131 patients will be needed in each study arm. To account for dropouts, incomplete procedures, and inadequate preparation, an additional 10% will be enrolled. Therefore, a total of 292 patients (146 patients in each group) will be enrolled.

Statistical analysis

Summary statistics will be presented as frequencies and percentages in the case of categorical variables and as the means with standard deviations (SD) in the case of continuous variables. Analysis will be performed by using an Intention-to-treat (ITT) approach. Interim analysis will be performed after enrollment of 131 patients. Student's *t*-test for continuous factors, Wilcoxon rank sum test for ordinal variables (such as polyp size), and Chi-square test for categorical variables will be used to assess differences in demographic and clinical characteristics of patients in each group. Factors associated with adenoma detection by the first examiner will be identified by univariate analysis. Factors with a *P* value <0.1 on univariate analysis will be further entered into forward stepwise logistic regression analysis. The adjusted odds ratio with 95% confidence interval (CI) will be used to describe the

influence of various factors on adenoma detection. All statistical analyses will be performed by using SAS version 9.3 or later (SAS Institute Inc., Cary, NC, USA). The criterion for statistical significance will be P value <0.05 .

REFERENCES:

6. le Clercq CM, Bouwens MW, Ronagh EJ, et al. Postcolonoscopy colorectal cancers are preventable: a population-based study. *Gut* 2014;63:957-963.
7. van Rijn JC, Reitsma JB, Stoker J, Bossuyt PM, van Deventer SJ, Dekker E. Polyp miss rate determined by tandem colonoscopy: a systemic review. *Am J Gastroenterol* 2006;101:343-350.

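### Suction marks are equalised in the CO2 arm only, so a right colon without them may suggest water exchange to the blinded tandem examiner

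*Combined protocol and SAP*

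**What the plan says.** All references are to the combined protocol and SAP, Methods.

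- **Masking step (Colonoscopy Procedures).** For the CO2 arm, the instruction is that "suction marks will be deliberately produced in the hepatic flexure and cecum to mimic the same marks frequently produced by the WE technique". It covers the CO2 group with no stated exception. No counterpart is given for a WE patient who shows no marks.
- **Suction by arm (same section).** In WE, "When the cecum is reached and after most of the water is suctioned to collapse the cecal lumen, CO2 will be opened", which makes a cecal mark likely. For the other arm, "Cleaning in the CO2 group will be performed entirely during withdrawal".
- **Outcome assessor (same section).** "A tandem inspection of the right colon will then be performed by a second endoscopist blinded to the insertion method in both study groups". Every polyp found on that pass counts as missed.
- **Blinding check (same section).** At the end, "the second endoscopist will be asked at the end of tandem right colon examination to guess which insertion method has been used". The criterion is "If less than 66% of these answers are correct, then adequate blinding will be considered to have" been achieved. It is stated for all answers together.
- **Who examines.** Two colonoscopists perform the procedures, and randomization is stratified by colonoscopist. The plan does not say outright that the second endoscopist is the other of these two, but that is the natural reading.

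**The concern.** The plan itself treats suction marks as a trace of the insertion method that could tell the tandem examiner which arm the patient is in. It then removes the cue in one direction only. CO2 patients are marked by instruction, whereas WE patients are marked only when the technique happens to leave marks. If both colonoscopists perform first examinations, the tandem examiner has made these marks in other patients and knows the rule. To that examiner, a colon missing marks at either site points towards WE.

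This matters because the same examiner generates the numerator of the primary outcome. If search on the tandem pass were less thorough in patients believed to be WE, fewer missed lesions would be found in them and the WE miss rate would fall for a reason unrelated to the technique.

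**Working it through.** **Inputs**
- Allocation 1:1 (Randomization).
- 146 patients per arm (Sample size estimation). This reproduces: 131 / 0.90 = 145.6, rounded up to 146, or 292 in total.
- Blinding threshold of 66% correct guesses (Colonoscopy Procedures). This is a chosen criterion, so there is nothing to re-derive.
- c = share of CO2 patients with visible marks at both sites on the tandem pass. Read literally, the instruction gives c = 1. The plan states no adherence check.
- f = share of WE patients with marks at both sites. The plan says only that marks are frequent, so the range 0.50 to 0.95 is an assumption.

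**Formulas**
- WE patients without a full set of marks = 146 × (1 − f).
- P(WE | not fully marked) = (1 − f) / [(1 − f) + (1 − c)].
- Correct guesses if the examiner says WE when marks are missing and CO2 otherwise = [c + (1 − f)] / 2. With c = 1 this is 1 − f/2.
- Correct guesses if the examiner says WE when marks are missing and tosses a coin otherwise, with c = 1: 0.75 − 0.25f.

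**Results with c = 1**

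| f | WE patients not fully marked, of 146 | Correct, guessing from marks | Correct, coin toss when marked |
|---|---|---|---|
| 0.95 | 7 | 52.5% | 51.25% |
| 0.90 | 15 | 55% | 52.5% |
| 0.80 | 29 | 60% | 55% |
| 0.70 | 44 | 65% | 57.5% |
| 0.50 | 73 | 75% | 62.5% |

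**Against the 66% criterion.** Guessing from marks stays under it when 1 − f/2 < 0.66, that is, f > 0.68. With a coin toss for marked patients it stays under when 0.75 − 0.25f < 0.66, that is, f > 0.36. The check can therefore pass with just under 32% of the WE arm recognisable in the first case (1 − 0.68) and just under 64% in the second (1 − 0.36).

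**If CO2 marking is incomplete or fades.** At f = 0.90, P(WE | not fully marked) is:
- c = 0.98: 0.10 / (0.10 + 0.02) = 83%
- c = 0.95: 0.10 / (0.10 + 0.05) = 67%
- c = 0.90: 0.10 / (0.10 + 0.10) = 50%, which is no information

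**If marks are equally frequent in both arms (c = f).** An unmarked colon carries no information, and guessing from marks is 50% correct whatever f is.

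**The case against.** The strongest reply is that the plan already tests its blinding and watches tandem effort. It asks the second endoscopist to guess the method, and under Definition it records inspection times for both endoscopists and compares them between groups. Guessing from marks at f = 0.90 or 0.70 would meet the plan's own criterion. WE suction collapses the cecal lumen, so nearly all WE patients may carry a cecal mark and f may be close to 1.

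Part of this stands. The leak may be negligible, and the plan is not blind to the risk. But both checks measure after the event and prevent nothing. A pooled percentage can look acceptable while a recognisable subset sits inside one arm, and inspection time is only a proxy for thoroughness. The collapse step concerns the cecum; no equivalent is described for the hepatic flexure, where marks are also mimicked. Mark presence is not among the listed data items, so the sponsor could not readily show that the two arms match.

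Three stronger readings go beyond the documents:
- *An unmarked colon identifies WE with certainty.* That requires marks at both sites in all CO2 patients, still visible after a first withdrawal with cleaning and polypectomy. The text is a group-level instruction and establishes neither adherence nor visibility. Inferring WE from a mark missing at just one site is weaker still, since one faded CO2 mark defeats it.
- *Blinding has failed.* Nothing in the documents gives f or any guess results.
- *The miss rate is biased in favour of WE.* An examiner who suspects WE might search less, more or just the same. No effect on the miss rate can be estimated.

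**Conclusion.** The point holds as a one-sided masking step that leaves a possible unblinding cue, of unknown size, for the examiner who determines the primary outcome. If all CO2 patients are visibly marked, the WE patients affected number about 7 of 146 at f = 0.95, 15 at 0.90 and 44 at 0.70. The cue shrinks as CO2 marking becomes incomplete and vanishes if the two marking rates happen to coincide. The 66% criterion does not settle the matter, because it would pass at f = 0.70.

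This rests on three assumptions: the tandem examiner is one of the two colonoscopists and knows the rule; the CO2 instruction is largely followed; and some WE patients lack marks at one or both sites, as the plan's own wording implies. It is a design gap worth closing because closing it is cheap. It is not evidence that the result is biased.

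**What to change.** 1. **Same step in both arms.** Add a sentence to Colonoscopy Procedures: before handing over, the first endoscopist ensures that suction marks are present at both the cecum and the hepatic flexure in every patient, adding them in WE patients who lack them. The reinsertion to the cecum, already done under CO2 in both groups, is a natural moment. This removes mark presence as a cue whatever f is.
2. **Record it.** Note for each patient and site whether marks were present at handover and whether any were added. For patients already treated, code mark presence from the procedure recordings the plan already requires, as far as they show it.
3. **Report it.** Give the second endoscopist's guesses by arm and by mark status alongside the pooled 66% criterion.
4. **Keep the primary comparison whole.** Do not drop unmarked WE patients, even though that may look like a natural sensitivity analysis. It would be a post-randomisation exclusion in one arm. Marks plausibly reflect how suction was applied, which is part of the WE technique, so a changed result could not be attributed to unblinding.

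The cost is one sentence, an extra data item and a few seconds in some procedures. The small downside is that WE patients without marks receive the same superficial mark already made in CO2 patients.

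### The size criterion for advanced adenoma (larger than 10 mm) does not match the plan's own large-polyp class (10 mm or more), so some 10 mm adenomas may not count in two secondary outcomes

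*Combined protocol and SAP*

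**What the plan says.** All the definitions stand in the Definition section under METHODS.

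- Size classes: "Small polyps will be defined as polyps with size 6-9 mm" and "Large polyps will be defined as polyps with size ≥ 10 mm". Diminutive polyps are those up to 5 mm.
- Advanced adenoma: "Advanced adenomas will be defined as those lesions with one of the following criteria". Criterion 1 is "lesions larger than 10 mm in diameter". The others are "2) lesions with a villous component; 3) lesions with high-grade dysplasia; and 4) lesions with invasive features", and none of these three carries a size limit.
- Outcome: "Advanced ADR will be defined as the proportion of colonoscopies with at least one advanced adenoma".

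Study Outcomes lists "overall advanced ADR, right colon advanced ADR" among the secondary outcomes. On measurement, Colonoscopy Procedures says "Polyp size will be determined by comparison with an opened biopsy forceps or a snare". It gives no rule for precision or rounding.

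**The concern.** Two rules in the same section divide lesions at 10 mm, but one includes that value and the other excludes it. The plan neither explains the difference nor says that it is intended.

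The value in question is one that will be recorded. The size classes leave no place for 5.5 or 9.5 mm, which points to whole-millimetre sizes, and size is judged by eye against an instrument. Clustering at a round value such as 10 mm is plausible, although the documents do not quantify it.

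Two things are at stake. First, the definition decides which colonoscopies count as positive for two named secondary outcomes. Second, an analyst could follow the literal text or take the large class as the size criterion. If this is not settled beforehand, the choice could be made after the data have been seen. A report could also show more adenomas in the large class than meet criterion 1, with nothing in the plan to explain the gap.

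**Working it through.** The plan states no figure that depends on this cut-off, so there is none to reproduce. The check applies the written rules to lesions on either side of the boundary.

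**Step 1: lesion level.** Inputs are the large-polyp definition (10 mm or more) and the four advanced-adenoma criteria, any one of which suffices. Both come from the Definition section. Feature means a villous component, high-grade dysplasia or invasive features.

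| Adenoma size | Feature present | Large | Advanced, as written (>10 mm) | Advanced, if ≥10 mm |
|---|---|---|---|---|
| 9 mm | no | no | no | no |
| 9 mm | yes | no | yes | yes |
| 10 mm | no | yes | **no** | **yes** |
| 10 mm | yes | yes | yes | yes |
| 11 mm | no | yes | yes | yes |
| 11 mm | yes | yes | yes | yes |

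Only the third row changes with the cut-off.

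**Step 2: colonoscopy level.** Advanced ADR counts colonoscopies, not lesions. A third-row lesion changes overall advanced ADR only if that colonoscopy has no other advanced adenoma. It changes right colon advanced ADR only if the lesion lies in the right colon and no other advanced adenoma is found there.

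**Step 3: possible size.** The documents do not give the inputs, so this step is an illustration. Two values are assumed:

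- 8% of the 146 patients planned per arm have an adenoma of 10 mm or more: 0.08 × 146 = 11.7, or about 12 patients.
- 20% to 40% of such adenomas are recorded at exactly 10 mm: 0.20 × 12 = 2.4 and 0.40 × 12 = 4.8.

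That is about 2 to 5 patients per arm, or 2.4/146 = 1.6 to 4.8/146 = 3.3 percentage points of overall advanced ADR. The calculation applies a share of lesions to a count of patients, which is valid only with one such adenoma per patient. On that footing it is a ceiling, because it deducts nothing for 10 mm adenomas that qualify on histology or for patients with another advanced adenoma. It gives no separate figure for the right colon.

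**Step 4: what does not depend on the cut-off.** The primary outcome, the combined right colon adenoma and hyperplastic polyp miss rate, has no size threshold. Nor do ADR and the mean-adenoma measures. The sample size rests on the miss rate and is unaffected.

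**The case against.** The strongest reply is that nothing here is contradictory. The large class is a size band for polyps of any histology, whereas advanced adenoma is a separate composite for adenomas. Nowhere does the plan say that every large adenoma must be advanced, and both rules can be applied to every lesion. That stands: this is an unexplained mismatch of cut-offs, not a logical conflict. To say that the written rule discards events also presumes that a 10 mm adenoma ought to count, and the documents do not show which cut-off was intended.

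Three stronger readings are tempting, and the documents support none of them.

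- A reader might infer that an advanced adenoma must exceed 10 mm, so that all 10 mm lesions are lost. The wording "Advanced adenomas will be defined as those lesions with one of the following criteria" makes size one route among four.
- A reader might take the 2 to 5 patients per arm as an expected loss. Neither input behind it comes from the documents.
- A reader might infer bias between the arms. The same definition applies to both, and nothing in the plan shows that it would act differently in one of them.

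It can also be said that recorded sizes allow either version to be computed later. That is true. It makes the correction easy, but it does not say which version is the planned outcome.

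**Conclusion.** The mismatch is real, and nothing elsewhere in the document resolves it. Its reach is narrow: adenomas recorded at exactly 10 mm, with none of the three histological features, in colonoscopies with no other advanced adenoma (none other in the right colon, for the right colon outcome).

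The effect on the two advanced ADR outcomes cannot be computed. Clustering at 10 mm is an inference from the method of measurement, and the illustrative patient count is a ceiling on assumed inputs. This is a minor correction to an outcome definition. It matters mainly because it closes an open analysis choice and makes the size classes and the advanced ADR agree.

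**What to change.** Before analysis, reword criterion 1 as *10 mm or more in diameter*, to match the plan's own large class. Derive the size classes and advanced adenoma from the same recorded size variable.

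If the stricter cut-off is intended, state that in the Definition section, and report overall and right colon advanced ADR under the 10 mm or more cut-off as a sensitivity analysis.

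The cost is one phrase in the definition. Polyp size, histology and location are already recorded, so no new data, patients or procedures are needed, and the sample size stays as it is.
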